**Participants:**

Participants will be recruited from one adult acute care hospital (West Kendall Baptist Hospital) within Baptist Health South Florida (BHSF) health system; one of the largest not-for-profit hospital systems in South Florida. Initial screen will occur during the first 24-48 hours of the Medical/Surgical admission. Inclusion criteria: (1) admitted to the Medical/Surgical unit within the last 24 to 48 hours; (2) alert, awake, and oriented times three; (3) aged 21 years old and greater; (4) receiving her or his first peripheral intravenous potassium chloride replacement therapy as ordered by her or his physician or ARNP as part of her or his care and regardless of research; and (5) potassium level of 3.5 mmol/L or less. Exclusion criteria: (1) patients who have been in the Medical/Surgical unit for more than 48 hours; (2) altered mental status defined as not being alert, awake, and oriented times three; (3) patients who have already received intravenous potassium chloride replacement during the current admission and with the current IV access; (4) patients receiving intravenous Potassium replacement therapy through a central line ; and (5) patients that are not ordered potassium replacement by her or his physician as part of their care while hospitalized.

The literature indicates that the rate of phlebitis for IV administration of toxic substances is substantially higher than with non toxic substances (OR = 5.1). We computed the sample size needed in relation to the main objective of comparing the rate of phlebitis in subjects being administered a toxic substance (Potassium IV replacement) to the rate of phlebitis in subjects receiving the same substance but with the addition of 4% sodium bicarbonate additive (to neutralize the toxicity). Using an alpha of 0.05 in a logistic regression assuming the occurrence of phlebitis without 4% sodium bicarbonate additive at 0.15 and a multiple correlation between the covariates of 0.2, a total sample size of 150 (75 patients per group) would have a power of 80% to detect an odds ratio of 5.0.

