This sample size will yield an 80% power to detect a difference as little as 1.5 unit on a 10-point rating scale with unequal variances between the two groups, assuming a ratio of 2.75 between the groups' standard deviations in a Satterthwaite t-test at a two-sided 0.05 level of significance. It will also yield a power of 80% to detect an effect size of 0.46 in the length of administration using a t-test with a 0.05 two-sided level of significance. A sample size of 75 per group will also yield 80% power to detect a probability of 0.632 that an observation in the experimental group is less than an observation in the control group for the frequency of changing the IV, the number of nursing interventions and the rates of attrition using Wilcoxon rank-sum test with a 0.05 two-sided significance level. In addition, considering that currently about 85 patients per month receive IV potassium replacement on the Medical/Surgical floor, it is expected that the research team will be successfully able to enroll the needed sample. Although by power analysis a total of 150 participants is needed, in order to control for confounding variables the sample will be 200 (100 in each group).

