## **Tentative Plan for Data Analysis**

Descriptive statistics for demographic and baseline variables will be computed for both groups using frequencies and proportions for categorical variables and means, medians, standard deviations and ranges for numerical variables. To compare the differential rate of phlebitis between the two groups, we will compute the odds ratio (with a 95% confidence interval) using logistic regression. Although the randomization process aims at eliminating the differences between groups, if the groups end up significantly different in baseline variables, those variables will be controlled in the logistic regression. It

is hypothesized that the variances in pain scales will be different between the two groups. Therefore, to compare the pain level between the groups, we plan on using a Satterthwaite t-test. An independent t-test will be used to compare the length of administration per unit of the medication. All other variables will be compared between groups using Wilcoxon rank-sum tests. All tests will be performed at the 0.05 level of significance unless otherwise specified using Stata 12.1 (StataCorp, Texas).

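### The phlebitis odds ratio has no interval type or sparse-data method named: default Wald inference would cost about 4.5 points of power at 100 per group, and zero additive-arm events would leave no estimate

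*Combined protocol and SAP*

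**What the plan says.** The Tentative Plan for Data Analysis gives one analysis for phlebitis: "we will compute the odds ratio (with a 95% confidence interval) using logistic regression". If baseline variables turn out significantly different between groups, "those variables will be controlled in the logistic regression". On level and software it adds: "All tests will be performed at the 0.05 level of significance unless otherwise specified using Stata 12.1". It does not say whether the interval is Wald, profile-likelihood or exact, and it has no rule for an arm with few or no events.

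The sample-size text under Participants fixes the expected sparsity: "Using an alpha of 0.05 in a logistic regression", "assuming the occurrence of phlebitis without 4% sodium bicarbonate additive at 0.15", with "a multiple correlation between the covariates of 0.2", and "a total sample size of 150 (75 patients per group) would have a power of 80% to detect an odds ratio of 5.0". The same section then raises enrolment: "in order to control for confounding variables the sample will be 200 (100 in each group").

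**The concern.** Logistic regression reported as an odds ratio with a 95% interval usually means maximum likelihood with Wald limits. When one arm has only a handful of events, the Wald standard error is dominated by the reciprocal of that small count. The test then becomes conservative exactly where the treatment works well. At zero events the estimate diverges and the Wald interval does not exist.

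Two things are at stake: some power on the main objective, and the ability to report the planned odds ratio in the most favourable outcome, no phlebitis at all with the additive. If the method is chosen only after an empty cell is seen, it becomes a post hoc change to the main analysis.

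**Working it through.** **Inputs.** Control rate 0.15, odds ratio 5.0, alpha 0.05, 75 per group for power and 100 per group for enrolment (Participants). The odds ratio is read as protective because the additive is meant to reduce phlebitis.

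**Step 1: additive-arm rate.** Odds without additive = 0.15/0.85 = 0.1765. Divided by 5 this is 0.0353. Rate = 0.0353/1.0353 = 0.0341.

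**Step 2: the plan's own power figure.** For two proportions with pooled null variance, mean rate (0.15 + 0.0341)/2 = 0.0920 and difference 0.1159:

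z = [√75 × 0.1159 − z_α × √(2 × 0.0920 × 0.9080)] / √(0.15 × 0.85 + 0.0341 × 0.9659)

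One-sided 0.05 gives z = 0.827 and power 79.6%, which matches the stated 80%. Two-sided 0.05 gives z = 0.505 and power 69.3%. The inputs are therefore the ones the plan used. Sidedness is a separate question and is not part of this point. Everything below is two-sided, in keeping with the planned 95% interval.

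**Step 3: expected events.**
- 75 per group: 75 × 0.15 = 11.3 control and 75 × 0.0341 = 2.6 additive.
- 100 per group: 15 control and 3.4 additive.

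**Step 4: chance of no additive-arm events.** 0.9659^75 = 7.4%; 0.9659^100 = 3.1%.

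**Step 5: exact power without covariates.** The two binomials are summed over every possible pair of counts (x control, y additive).
- Wald: log odds ratio divided by √(1/x + 1/(n−x) + 1/y + 1/(n−y)), compared with 1.96. An empty cell counts as no estimate and so as not significant.
- Firth: with two groups the penalty adds half an event and half a non-event to each arm, so the fitted rate is (x + 0.5)/(n + 1), or (x + y + 1)/(2n + 2) under the null. Twice the difference in penalised log-likelihood is compared with 3.84.

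| Per group | Wald | Firth profile | Gap | Ordinary likelihood ratio | Fisher |
|---|---|---|---|---|---|
| 75 | 59.6% | 71.4% | about 12 | 74.2% | 62.2% |
| 100 | 79.2% | 83.7% | about 4.5 | 85.3% | 77.8% |

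An example at 100 per group is 7 events against 1. The log odds ratio is ln[(7/93)/(1/99)] = 2.008, its standard error √(1/7 + 1/93 + 1 + 1/99) = 1.079, and Wald z = 1.86, not significant. Firth's test is significant for this table.

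**Step 6: where the gap comes from.** With no additive-arm events, Firth's test is significant from 5 control events upwards, so nearly every such trial is a Firth success and a Wald failure. These trials supply about 3.1 of the 4.5 points at 100 per group, leaving about 1.4. At 75 they supply about 7.4 of 11.9, leaving about 4.5. The power loss and the missing estimate are therefore largely the same event and should not be added together.

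**Step 7: type I error.** Over common rates from 2% to 20%, Firth's test stays at or below about 5.0%. Wald is 3.6% to 4.5% at common rates of 10% to 15%. The ordinary likelihood-ratio test runs from about 6.5% to 9.5% at common rates of 2% to 5%.

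**Step 8: dependence on the control rate (odds ratio 5).**

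| Control rate | Gap at 75 (points) | Gap at 100 (points) |
|---|---|---|
| 10% | 23 | 16 |
| 15% | 12 | 4.5 |
| 20% | 5.0 | 1.6 |
| 60% | 0 | 0 |

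The 60% row uses the figure quoted under Significance for phlebitis and pain at 10 mEq/h.

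**The case against.** **The plan never says Wald.** This stands. The loss belongs to Wald inference, not to logistic regression. A reader might infer that ordinary logistic regression itself costs power, but the likelihood-ratio test from the same fit has 74.2% and 85.3%, above Firth. Part of that advantage reflects its looser type I error at low rates. The power figures are conditional on the assumed default. The infinite estimate at zero events is not: it follows from maximum likelihood under any interval method.

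**The loss is small in the trial as planned.** This also stands. Enrolment is 100 per group, so a reader should not take 12 points as the expected loss. That figure needs the analysed number to fall to 75, for instance through the removals described under Data Collection, and the documents give no expected removal rate.

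**The gain depends on the comparator.** True. At 100 per group Fisher's test (77.8%) is slightly below Wald, and Firth's estimate with Wald limits gains only 1.0 point. The benefit needs Firth together with the penalised profile likelihood.

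**Covariates.** A reader might infer that adjusting a model with 14 to 18 events makes the power loss worse. The simulations do not show this. With one covariate correlated 0.2 with group the gaps were 10.8 and 4.9 points (75 and 100 per group). With three prognostic covariates they were 8 (67% against 75%) and 3 (83% against 86%).

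**The stated analysis is valid, and the plan is headed as tentative.** Agreed. Wald errs on the conservative side, and an empty cell would be obvious when it occurred. That limits the seriousness of the point but does not remove the reason to settle the method in advance.

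**Conclusion.** The point holds as a cheap improvement to the analysis of the main objective. On the plan's own 15% rate and odds ratio of 5, and assuming Wald limits, the cost at the planned 100 per group is about 4.5 points of two-sided power. Most of it arises in the 3.1% of trials with no additive-arm events, where no finite odds ratio or Wald interval would be available. At 75 analysed per group the corresponding figures are about 12 points and 7.4%.

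The size rests on three assumptions: the protective reading of the odds ratio, Wald as the unstated default, and the 15% control rate. At 100 per group the loss is about 16 points if that rate is 10%, 1.6 points if it is 20%, and nil at 60%. The documents do not support reading this as a false-positive problem or as a fault of logistic regression in general.

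**What to change.** In the Tentative Plan for Data Analysis, state that the phlebitis logistic model, with or without covariates, is fitted by Firth's penalised likelihood, and that the p-value and 95% confidence interval come from the penalised profile likelihood. The comparison, data and sample size stay the same, and the result is finite with an empty cell. For example, 15 events against 0 at 100 per group gives (0.5/100.5)/(15.5/85.5) = 0.027.

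If the software does not offer this, name exact logistic regression as the fallback. Do not name the ordinary likelihood-ratio test, given its type I error at low event rates (step 7).

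The cost is one sentence and possibly an add-on command. The penalised odds ratio is pulled slightly towards 1: the median log odds ratio is −1.55 to −1.60 against a true −1.61, where maximum likelihood gives −1.70 to −1.73. The exact fallback is likely to be conservative. Without covariates it corresponds to Fisher's test, so it deals with the empty cell but does not recover the power.

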**Significance:**

Hypokalemia, or the low concentration of potassium (below 3.5 mmol/l), is a condition that can result in serious adverse effects including disturbances in cardiac conduction along with muscle, kidney,

gastrointestinal tract, genitourinary tract, respiratory, and endocrine dysfunction (Asmar, Mohandas, & Wingo, 2012; Hemstreet, et al., 2008). Hypokalemia is typically a result of chronic medical conditions such as reduced intake of potassium, chronic diuretic therapy, diarrhea, short bowel syndrome, vomiting and burns. Although potassium can be replaced orally, IV potassium chloride is utilized in patients that need rapid replacement, are showing clinical signs of low potassium, or patients who are unable to orally ingest the replacement. Potassium should always be diluted and slowly administered to reduce the likelihood of pain from inflammation of the vein or phlebitis. (Pharmacology for the Prehospital Professional, 2011). Yet, even at slow rates of 10 mEq/h phlebitis and pain have been reported in 60% of patients (Stephens et al., 1976).

Peripheral venous cannulation (PVC) is a common procedure carried out in hospital to allow rapid and accurate administration of medication (Endacott et al., 2009). In replacing Potassium intravenously, nurses need to have intravenous access. In WKBH 3 South/3 North/4 South Medical-Surgical Telemetry units, nurses often receive orders for Potassium replacement through Intravenous route. The majority of these patients have peripheral intravenous access. The intravenous access is often started in the Emergency Department and continued once the patient is admitted. The peripheral intravenous site is being assessed per protocol for phlebitis once per shift and as needed.

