#### Enrollment Process:

- (1) The study will be explained, consent and HIPAA; in either English or Spanish (which will be determined by the participant's personal choice), will be obtained (please see attached consent) after the principal investigator or designated key personnel has answered all questions. The potential participant will be provided with about 10 minutes of individual time to review the consent. Each participant will be provided a copy of their signed consent (please see attached).
- (2) Once enrolled the principal investigator or designated key personnel will: (a) contact the pharmacy to inform them that a new participant has been enrolled in the research study; (b) place a sticker on the chart of the participant (study number and enrollment date); and (c) place the participant (medical recorder number and study number provided by pharmacy) into the enrollment log. The pharmacy research team member will then randomize the participant into either the experimental group (4% sodium bicarbonate additive during peripheral intravenous potassium chloride replacement therapy) or the control group (standard of practice of no 4% sodium bicarbonate additive during peripheral intravenous potassium chloride replacement therapy) based on a randomization table. The randomization table will be generated by the statistician research team member after IRB approval is obtained by use of the statistical package nQuery. The pharmacy research team member will label the potassium replacement IV bags with a sticker to identify them as study participants. This will include the standard of practice of labeling the IV bags as potassium replacement and also a label stating "neut study participant" but without the designated grouping in order to maintain blinding. In order to maintain integrity of data and reduce bias the participant and direct patient care nurse will not be informed of randomization results. The pharmacy research team member will maintain a record of randomization that will be provided to the principal investigator.

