  - a. Participants enrolled in the control group will receive standard of practice which is intravenous potassium replacement without the 4% sodium bicarbonate additive at the rate ordered by the ordering physician or ARNP for peripheral intravenous potassium chloride replacement therapy which will be part of the care of the patient regardless of research, and based on the WKBH policy of potassium chloride infusion of no more than 100ml/hr. Pharmacist prepares, as standard of practice, each bag of 100 ml normal saline (NS) with 10mEq potassium chloride.

- b. Participants enrolled in the experimental group (4% sodium bicarbonate additive during peripheral intravenous potassium chloride replacement therapy) will receive the additive after pharmacy and/or the designated key personnel ([name]) coordinates the ordering of 4% sodium bicarbonate additive during peripheral intravenous potassium chloride replacement therapy. Pharmacist prepares, when ordered as standard of practice, each bag of 100 ml NS with 10mEq Potassium Chloride and 5 ml of 4% sodium bicarbonate additive, therefore, this practice will be used for the experimental group. The rate of peripheral intravenous potassium chloride replacement therapy will be ordered by the ordering physician or ARNP, for IV potassium chloride replacement therapy which will be part of the care of the patient regardless of research, and based on the WKBH policy of potassium chloride infusion of no more than 100ml/hr.

[figure not shown]
Data Collection:

- (1) Demographics (please see attached) will be collected by the principal investigator or designated key personnel after enrollment of patient.
- (2) peripheral intravenous potassium chloride replacement therapy (please see attached) data collection form: assessment of peripheral IV insertion site for phlebitis, using the VIP tool, and pain, using the Likert 11 point scale will be collected at baseline (prior to any peripheral intravenous potassium chloride replacement therapy), at 15 minutes after infusion started, every hour until peripheral intravenous potassium chloride replacement therapy is complete, and then at completion of replacement.

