or requesting for the infusion not to have an additive. In this case, or in any adverse event, the pharmacist will unblind the patient and the nurse by revealing which group the patient is in.

Data Storage:

- (1) All data collection sheets will be coded and not include identifying information.
- (2) The enrollment log(s) will be kept by the research team members in their locked BHSF office drawer or filing cabinet. At the end of the study the enrollment logs will be housed in the principal investigator's locked office drawer or filing cabinet. Enrollment logs will be kept separate from data collection. Peripheral intravenous potassium chloride replacement therapy data collection will be sealed in an envelope and placed in the designated 'research' box in the medication room. Then on a weekly basis the envelopes will be collected by a member of the research team and given to the co-investigator ([name]). Data entry into the BHSF password protected computer system will be done by the designated research team member and then all hard copies will be housed in the principal investigator's BHSF locked office or filing cabinet.
- (3) All demographic and chart review data will be given to the co-investigator ([name]). Data entry into the BHSF password protected computer system will be done by the designated research team member and then all hard copies will be housed in the principal investigator's BHSF locked office or filing cabinet.
- (4) At the end of the study, all data will be housed in the principal investigator's locked BHSF office drawer or filing cabinet.
- (5) All electronic data will be password protected on the BHSF computers of the research team.
- (6) All data will only be accessible by the research team.

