## **Other Pertinent Information:**

*Standard of Practice for Potassium chloride replacement therapy:* The Physician or ARNP evaluates the Potassium level of the patient and orders potassium replacement therapy for potassium level of 3.5 or below. The amount of replacement of potassium intravenously is determined by the patient's physician or ARNP based on patient's condition and potassium level as standard of practice and the order is provided to the direct patient care nurses and pharmacy. Patients with peripheral IV access may be ordered to receive intravenous potassium replacement therapy of 10 mEq/100 ml Normal Saline bag, ordered as one or multiple doses depending on the potassium level and patient's condition. The peripheral intravenous site is being assessed per protocol for phlebitis once per shift and as needed. During potassium chloride intravenous replacement direct patient care nurses can initiate nursing interventions including but not limited to: changing IV site, slowing rate of infusion, and requesting from the patient's physician or ARNP an order for 4% sodium bicarbonate additive solution.

*Study Procedures covered:* Those participants in experimental group who will receive up to 4 doses of 4% sodium bicarbonate will not be charged for those experimental doses. The Academy of Medical-Surgical Nurses (AMSN) is sponsoring this study and the cost of 4% sodium bicarbonate to Pharmacy will be covered by AMSN.

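### Covariates enter the phlebitis model only when randomized groups differ significantly on them, so the covariate set is not fixed in advance; the pain test leaves out the baseline score (minor)

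*Combined protocol and SAP*

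**What the plan says.** Tentative Plan for Data Analysis compares phlebitis by logistic regression, giving an odds ratio with a 95% confidence interval. On covariates it says that "if the groups end up significantly different in baseline variables, those variables will be controlled in the logistic regression". It names no variable, no baseline test and no separate threshold. The general rule is "All tests will be performed at the 0.05 level of significance unless otherwise specified", which I take to cover the baseline tests as well.

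For pain, the same section says: "to compare the pain level between the groups, we plan on using a Satterthwaite t-test". It gives no baseline term, change score or time point. The covariate rule is confined to the logistic regression, so even a significant imbalance in baseline pain would not bring that score into the pain comparison.

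Data Collection, item 2, records both the visual infusion phlebitis (VIP) score and pain before treatment: they "will be collected at baseline (prior to any peripheral intravenous potassium chloride replacement therapy), at 15 minutes after infusion started", then hourly and at completion.

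The sample-size text under Participants assumes a multiple correlation of 0.2 between covariates and raises the total from 150 to 200 to allow for confounding, again without naming a variable.

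**The concern.** Adjustment is useful when a covariate predicts the outcome. A significance test between randomized arms does not measure that; it picks out chance imbalance. The rule therefore leaves out most real predictors and admits irrelevant variables at the same rate. Whether a chance imbalance in a real predictor is corrected depends on which side of p = 0.05 it falls.

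The odds ratio also changes meaning with the covariates it is conditional on. A reader of the plan cannot say which odds ratio will be the main result until the arms have been compared at baseline.

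For pain, what is at stake is only precision: a measurement already made before infusion is not used.

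**Working it through.** **1. The plan's own figure.** Participants gives 150 in total for 80% power (control rate 0.15, odds ratio 5.0, multiple correlation 0.2, alpha 0.05). The two-sided two-proportion formula, inflated by 1/(1 - R²) with R² = 0.04 or 0.2, gives 67 to 80 if the odds ratio is read upward and 203 to 243 if it is read as protective. The nearest match is 152: protective, one-sided, no inflation. With all stated inputs, 150 is not reproduced. That is a separate matter and nothing below depends on it. From that section I use only 0.15, 5.0, the SD ratio of 2.75 and 100 per group.

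**2. How often the trigger fires.** Each variable enters with probability 0.05. For k independent variables the chance that at least one enters is 1 - 0.95^k: 23%, 40% and 64% for k = 5, 10 and 20. The documents do not give k. With two candidates the chance that none enters is 0.95² = 90%.

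**3. What stays unadjusted.** At 100 per group the largest non-significant imbalance in a continuous variable is 1.972 × √(2/100) = 0.279 SD. Left alone, it shifts the odds ratio by a factor of (predictor odds ratio per SD)^0.279. For assumed predictor odds ratios of 1.3, 1.5 and 2.0 this is 1.08, 1.12 and 1.21.

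**4. Power and type I error (simulated).**
- Protective reading: odds (0.15/0.85)/5 = 0.0353, so the additive-group rate is 0.034.
- Setting: 100 per group, Firth-penalized test under both rules, two covariates. Baseline VIP was above 0 in 5-10% of patients with odds ratio 1 or 3; potassium had odds ratio 1 to 2 per SD. All of these strengths are assumed.
- Power was 0.828-0.847 with the trigger and 0.826-0.855 with fixed covariates. The difference ran from -0.8 to +1.5 points (paired standard error 0.2-0.3 points). With VIP alone it was -0.1 to +0.5.
- With two normally distributed predictors at odds ratio 1.5, 2.0 and 2.5 per SD, the gain was 0.6, 2.2 and 3.8 points.
- Null rejection was 0.044-0.054 with the trigger and 0.047-0.054 with fixed covariates.

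**5. Meaning of the odds ratio.** In a simulation at 75 per group with one strong assumed covariate (log odds ratio 1 per SD) and a conditional odds ratio of 3, the median estimate was 2.57 unadjusted and 3.06 adjusted.

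**6. Number of events.** At 100 per group: 15 + 3.4 = 18.4 if odds ratio 5.0 is protective and fully realised; 15 + 15 = 30 with no effect; 15 + 46.9 = about 62 if 5.0 is read upward (rate 0.469). In the first case the chance of no event in the additive group is 0.9659^100 = 3.1%.

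**7. Pain.** Assume equal baseline SDs and the same correlation ρ in both arms, with outcome SDs in ratio r = 2.75. Adjusting with a common slope multiplies the variance of the group difference by 1 - ρ²(1 + r)²/[2(1 + r²)] = 1 - ρ² × 14.0625/17.125 = 1 - 0.821ρ². For ρ = 0, 0.2, 0.4 and 0.6 this is 1.00, 0.967, 0.869 and 0.704, a reduction of 0, 3, 13 and 30%.

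In simulations on bounded integer 0-10 scores with 50, 80, 90 and 95% of baseline scores at 0, the reduction was 10, 6, 4 and 2%. At zero correlation, HC3 variance averaged 1.02 times the Satterthwaite variance. HC3 null rejection was 0.047-0.055. HC3 was undefined in 0.1, 1.9 and 40% of trials at 95, 97 and 99% zeros, hence the fallback proposed below, with which null rejection was 0.048-0.051.

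**The case against.** The strongest case against is that little harm is shown. The power effect for plausible covariates is close to nil. The shift of 1.08 to 1.21 is the worst case just under the threshold, whereas with a standard error of about 0.607 the confidence interval spans a factor of exp(1.96 × 0.607) = 3.3 each way. This stands, and it is why the point is minor.

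The pain half also weakens on inspection. Baseline is taken before any potassium infusion, in patients having their first replacement, so site scores at or near 0 are plausible and the gain would then be a few percent. This stands too.

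The choice of covariates is open to challenge. Baseline VIP may vary, since "The intravenous access is often started in the Emergency Department and continued once the patient is admitted", but no VIP cutoff for phlebitis is given, so a baseline score above 0 might overlap the outcome. Potassium is not a listed data item ("All demographic and chart review data will be given to the co-investigator" does not say which data), and the documents tie its level to dosing ("ordered as one or multiple doses depending on the potassium level"), not to phlebitis. Both served above as illustrations; only the first is carried into the fix, with a condition.

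Stronger readings that a reader might infer are not supported:
- That the main model is undefined. Its form, effect measure and interval are fixed; only the covariate set is contingent.
- That the rule inflates false positives. The simulated null rejection does not show this.
- That it contradicts the sample-size text. The covariate allowance there can be read as room for contingent adjustment.
- That the unadjusted pain test is invalid. It is valid, only possibly less precise.

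The demographics form is an attachment not shown, so its absence is no fault of the plan. Listing items collected would in any case not name model covariates.

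**Conclusion.** The point holds as a minor one. The plan selects covariates for its main comparison by a test of chance imbalance, so a real predictor is adjusted for about 5% of the time and the conditioning of the main odds ratio is not known beforehand. The gain from changing this is pre-specification, not power: about -0.8 to +1.5 points for the illustrated pair. Omitting baseline pain costs between nothing and 30% in variance over correlations of 0 to 0.6, most likely at the low end if patients seldom have site pain before infusion. These sizes rest on assumed predictor strengths, prevalences and correlations, none of which the documents give, and on the 0.05 level applying to the baseline tests.

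**What to change.** **Phlebitis.** Delete the significance-triggered rule. In a dated document, written before any outcome data are examined, name one or two covariates expected to predict phlebitis, chosen from items already collected at baseline. Baseline VIP (0 versus above 0) is one example, provided that a baseline score above 0 does not itself meet the phlebitis definition. Include the covariates whatever their balance, and report the unadjusted odds ratio alongside. Tie the deadline to outcome data and not to unblinding, because "The pharmacy research team member will maintain a record of randomization that will be provided to the principal investigator" and no timing is given. Firth-penalized logistic regression is an option if events are few, subject to a check that Stata 12.1 offers it.

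**Pain.** At whichever score the investigators prespecify, use linear regression on group and baseline pain with HC3 standard errors. Keep the Satterthwaite t-test if fewer than 10 patients in the pooled sample have baseline pain above 0.

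**Cost.** Wording only, since VIP and pain are already recorded before infusion. The adjusted odds ratio is conditional and has a slightly larger standard error when covariates predict (median 0.607 to 0.623 with two predictors at odds ratio 2.0 per SD). Up to 0.8 points of power were lost in the settings tried. Pain adjustment costs about 2% in variance if baseline is uncorrelated with outcome.
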